11.1. Definitions

11.1.1. Adverse Events

An AE is any untoward medical occurrence in a subject administered a pharmaceutical product, biologic (at any dose), or medical device, which does not necessarily have a causal relationship with the treatment. Therefore, an AE can be any unfavorable and unintended sign (including an abnormal laboratory finding), symptom, or disease temporally associated with the use of a medical product, whether or not considered related to the medical product. Adverse events may include the onset of new illness and the exacerbation of pre-existing conditions.

The routine evolution of the disease condition under treatment according to the protocol will be evaluated as part of the disease symptoms assessments. Changes in Pompe disease symptoms must be reviewed by the investigator or a medically qualified sub-investigator and be recorded as “Clinically Significant” or “Not Clinically Significant” in subjects’ source records. Changes in the disease condition may not qualify as AEs. However, if there is a clinically relevant worsening of a sign or symptom of the condition under treatment and the outcome fulfills the definition of an AE, it must be reported as directed in the protocol.

Any AE that begins after the first dose of study medication (ATB200 and/or AT2221) will be considered a TEAE.

Subjects experiencing AEs should be followed until their health has returned to baseline status or stabilized or have otherwise been explained.

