10.1. Missing Adverse Event Onset Date, Intensity, and Relationship

10.1.1. Missing or Partial Adverse Event Onset Date or Medication Start Date

Complete dates will be imputed from partial dates of AEs and medications solely for the purpose of defining treatment emergence for AEs and prior/concomitant status for medications. Dates will be defined using the hierarchy of derivations below.

Algorithm for imputing missing or partial AE or medication start date:

1. If year is not missing and is after the year of first application of study drug:
If month is missing, then impute month as January.
If day is missing, then impute day as the first of the month.
2. If year is not missing and is the same as the year of the first application of study drug:
If month is missing, then impute month as the month of the first application of study drug.
If day is missing but month is the same as the month of first application of study drug, then impute day as the first day of study drug application.
If day is missing but month is after the month of first application of study drug, then impute day as the first of the month.
3. If year is missing, then impute the year as the year of the first application of study drug:
If month is missing, then impute month as the month of the first application of study drug.
If day is missing, then impute day as the day of the first application of study drug.
4. If the start date is completely missing, but the AE is either ongoing or the stop date is after the first date of drug application, then impute the start date as the first application of study drug.
5. If using the above rules, the stop date is before the start date, then leave the start date missing and assume that AE is treatment-emergent for the purpose of the analysis.

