10.3. Adverse Events

Treatment-emergent AEs (TEAEs) are defined as AEs whose onset occurs after receiving the study medication. Treatment-emergent AEs that occurred during Stages 1 and 2 have been reported in iCSR-1 and will not be repeated here unless the underlying data have changed.

The SAP describes the events that occurred starting from the administration of 20 mg/kg ATB200 + 260 mg AT2221 in Stage 2 Period 5 through Stages 3 and 4. Events which occur more than 30 days after the last dose of study medication will not be considered as treatment-emergent. Adverse events with an unknown date of onset and a stop date after the start of the study period or unknown will be included as TEAEs. Any AE with a start date equal to the date of first dose, where the time of the AE cannot definitively place the start of the AE prior to the first dose, will be considered as treatment-emergent. If any AE records contain only partial dates, these will be handled by imputation as described in Section 10.1.1. All AEs will be provided in data listings, and those that are treatment-emergent will be flagged in the listings.

Adverse events will be summarized using number and percentage as described in Section 6.2.1. Incidence rate of AEs by patient-years of exposure will also be summarized.

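### SAP 10.1.1 rule 5 counts an adverse event as treatment-emergent when its recorded stop date shows that it ended before first dose

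*SAP*

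**What the plan says.** SAP 10.1.1 gives five ordered rules for partial or missing AE onset dates.

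- **Rule 2** (onset year equals first-dose year): a missing month becomes the first-dose month. If the day is missing and the month is the first-dose month, "then impute day as the first day of study drug application".
- **Rule 3**: "If year is missing, then impute the year as the year of the first application of study drug". A missing month or day is also taken from the first dose.
- **Rule 4** (start completely missing): the first dose is imputed only if "the AE is either ongoing or the stop date is after the first date of drug application".
- **Rule 5** (stop before the resulting start): "then leave the start date missing and assume that AE is treatment-emergent for the purpose of the analysis".

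SAP 10.1.2 ends by ruling out any imputation of AE stop dates, so rule 5 compares an imputed start with a recorded stop.

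SAP 10.3 states: "Treatment-emergent AEs (TEAEs) are defined as AEs whose onset occurs after receiving the study medication". Protocol 11.1.1 agrees: "Any AE that begins after the first dose of study medication (ATB200 and/or AT2221) will be considered a TEAE". For a missing onset, SAP 10.3 adds that events with "unknown date of onset and a stop date after the start of the study period or unknown will be included as TEAEs". It sends partial dates to 10.1.1.

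**The concern.** An event that is over before the first dose cannot have started after it. When rule 5 fires because a recorded stop precedes an imputed first-dose start, the sensible inference is that the imputed start is wrong and the event came before treatment. Rule 5 discards the imputed start but keeps the conclusion it would have supported.

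Such a record would enter the TEAE tables by system organ class and preferred term, and the incidence rates per patient-year, as an event on 20 mg/kg ATB200 + 260 mg AT2221. Cohorts are small, so a single subject moves a percentage visibly. A programmer who follows both 10.1.1 and 10.3 also has two answers for the same record.

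**Working it through.** The plan gives no figure to reproduce. The check is a reading of the rules, a worked case and an enumeration.

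**Worked case (illustrative dates).** First dose 20 March 2016; onset recorded as March 2016 with no day; stop recorded as 15 March 2016.
1. Rule 2: same year, same month, day missing, so the imputed start is 20 March.
2. Stop (15 March) is before start (20 March), so rule 5 applies and the event is a TEAE.
3. SAP 10.3: the event ended 20 − 15 = 5 days before dosing, so its onset was not after study medication. With the start left missing, the stop is neither unknown nor after the period began, so the unknown-onset sentence does not bring it in.

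An onset recorded only as 2016 gives the same result, because rule 2 fills month and day from the first dose.

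**Such records can arise.** Protocol section 11 starts AE reporting at informed consent, and screening runs up to 28 days.

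**Enumeration.** The rules were coded as written and run over every onset day from 28 days before to 90 days after first dose, with durations of 0 to 30 days. Dates and durations are assumptions; the results are scenarios, not expected event counts.

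| Missing part of onset | Rule 5 triggers, first dose 20 March | Rule 5 triggers, first dose 10 January |
|---|---|---|
| Day | 190 | 45 |
| Day and month | 406 | 45 |
| Sum | 596 | 90 |

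In every one of the 596 and the 90, the stop date was before first dose. The counts can be checked by hand. With the day missing, onset must lie in 1–19 March (19 × 20 / 2 = 190) or 1–9 January (9 × 10 / 2 = 45). With the month also missing, all 28 pre-dose days are exposed for a March first dose (28 × 29 / 2 = 406). For a 10 January first dose, earlier onsets fall in the previous year, where no rule applies, leaving 45.

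**Exposed window.** Rule 2 has no branch for a day-missing onset in a month before first dose. For that pattern the window is only the earlier days of the first-dose month: 19 for a 20 March dose, at most 30. The full screening period is exposed only if the month is missing too and the recorded year is the first-dose year.

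**Cohort 1 anchor.** SAP 6.4.5 sets Visit 9 (Day 85) as the reference start day, and SAP 10.3 covers events from Stage 2 Period 5. SAP 10.1.1 refers only to the first application of study drug. Under a Visit 9 anchor, with day and month both missing, the outer bound is about 28 + (85 − 1) = 112 days, cut off at 1 January of the Visit 9 year. Under a Stage 1 Day 1 anchor, the 84 days of Stage 1 and Period 4 drop out.

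**Weight of one subject (planned sizes, SAP Table 2).** 100/n gives:
- Cohort 1 (n = 11): 9.1 points
- Cohort 2 (4–6): 25.0 to 16.7
- Cohort 3 (5): 20.0
- Cohort 4 (6–8): 16.7 to 12.5
- Total (11 + 4 + 5 + 6 = 26 to 11 + 6 + 5 + 8 = 30): 3.8 to 3.3

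**The case against.** **Assuming emergence is conservative.** SAP 10.1.3 likewise takes the worst case for missing intensity and relationship. That is sound when timing is in doubt. Here a recorded stop date removes the doubt, so the defence fails for these records.

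**SAP 10.3 states an inclusion, not an exclusion.** This is correct: the unknown-onset sentence says which events go in, and partial dates are routed separately to 10.1.1. The conflict does not rest on that sentence alone. The TEAE definition excludes an event that ended before dosing, and rule 4 applies the same stop-date test.

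**The effect is small and visible.** Each affected record needs a partial onset, a complete stop date and resolution before dosing. Protocol 11.4 requires start and end dates for every AE. There is no hypothesis testing, and the listings show dates and TEAE flags. The any-TEAE percentage rises only if the subject has no other TEAE. All of this stands and limits the importance of the point, but it does not make the rule right.

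**Completely missing starts may escape.** Rule 3 would impute the first dose, while rule 4 would not if the event stopped before dosing. The overlap is unresolved, so these cases (406 further scenarios at each example date if rule 3 governs) are left out of the totals above.

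**Rule 5 can also fire properly.** In unusual patterns, such as year missing with month known, it can fire with a stop on or after first dose. The TEAE assumption is reasonable there and should be kept.

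**Conclusion.** The point holds as a defect in a stated rule. In the two ordinary patterns, rule 5 classes an event that ended before dosing as treatment-emergent, contrary to SAP 10.3, Protocol 11.1.1 and rule 4. In those patterns the direction is certain, since the rule can only add TEAEs. The size is not known and may be nil.

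A reader might infer three stronger things that the documents do not support:
- **That TEAE counts are inflated.** The number of qualifying records is not given, so only the possibility is shown.
- **That every partially dated event in the 28 days of screening, or about 112 days for Cohort 1, is exposed.** Those spans need the month missing as well as the day. The longer one also needs the Visit 9 anchor.
- **That Cohort 1 events from Stage 1 and Period 4 are credited to the 20 mg/kg + 260 mg period and counted again after the first interim report (iCSR-1).** This follows only if the first application of study drug means Visit 9. SAP 6.4.5 and 10.3 point that way, but Protocol 11.1.1 points to the first dose of either drug, and 10.1.1 does not choose. It is an open risk.

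The correction should be made before database lock because the rule gives a wrong answer as written and is cheap to repair.

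**What to change.** Make two changes in SAP 10.1.1.

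1. State once, for all of rules 1 to 5, that the anchor is the first dose of the analysis period: Visit 9 for Cohort 1 and Day 1 for Cohorts 2, 3 and 4. Changing rule 5 alone would leave rules 1 to 4 on an undefined anchor and allow the two to differ.
2. Amend rule 5: if the recorded stop date is before that dose, the AE is not treatment-emergent; otherwise leave the start missing and treat the AE as treatment-emergent.

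The cost is a sentence for each change, one line of derivation code for rule 5, and a check that the programs use the same anchor throughout. No new data are needed. The amended rule drops no event that SAP 10.3 would count. Under the Visit 9 anchor it also keeps Cohort 1 events with a recorded stop before that visit out of the later tables.

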10.1.2. Missing or Partial Medication Stop Date

References to month are the month of the stop date:

1. If year and month are known and study medication stopped during that month and year, use the stop date of study medication.

2. If year and month are known and informed consent was provided during that month and year, use the date of informed consent.
3. If year and month are known and study medication stopped after the date of informed consent and not in the month that medication stopped, use the last day of the month.
4. If year and month are known and are prior to the month of informed consent, use the first day of the month.
5. If only year is known and study medication stopped during that year, use the stop date of study medication.
6. If only year is known and study medication stopped after that year, use December 31st of that year.
7. If only year is known and study medication stopped prior to that year, use the first day of the year.
8. Should any of the previous stop dates created be before a start date, either a complete date or an imputed one, use the (imputed) start date instead of the date that would otherwise be created.
9. Otherwise, if stop date is unknown, leave as missing.

No imputations will be applied to AE stop dates.

10.1.3. Missing Intensity and Relationship

If intensity is missing for any AE or TEAE, then its intensity will be classified as “severe” in the summary tables. If the assessment of relationship of the TEAE to study drug is missing, it will be classified as “related” in the summary tables.

However, in the data listings, the actual observed values will be reported. That is, if the response is missing, it will show as missing in the data listings.

10.2. Extent of Exposure and Compliance

The extent of exposure (duration of treatment) is defined as the number of days on treatment.

For Stages 1 and 2, duration will be calculated as (date of last dose – date of first dose + 1) / 30.4. The duration of exposure and compliance during Stages 1 and 2 were reported in iCSR-1 and will not be repeated here, as the data are not expected to change.

From Stage 2 Period 5 through Stages 3 and 4, duration is calculated as:

Duration (months) = (date of last dose in ATB200-02 as of the data cutoff date – date of first dose of 20 mg/kg ATB200 + 260 mg AT2221 study drug [in Stage 2 Period 5] + 1) / 30.4.

The study drug exposure and compliance starting from the first dose of the 20 mg/kg ATB200 + 260 mg AT2221 study drug in Stage 2 Period 5 will be summarized for ATB200 and AT2221 separately. Dose completion, treatment duration, and treatment compliance will be tabulated. A frequency distribution for the number of treated subjects and descriptive statistics for the duration of treatment (months) and compliance will be provided. The number and percentages of subjects will be tabulated by the extent of exposure categorized into months as: < 6, 6 to < 12, 12 to < 18, 18 to < 24, 24 to < 30, 30 to < 36, and \geq 36.

Compliance for each subject taking ATB200 will be calculated based on the number of infusions as well as the actual infusion dose administered. Compliance based on infusion dose is calculated as:

100 * (total infusion dose administered [mg/kg] / total infusion dose planned or intended [mg/kg]) starting from the first dose of the 20 mg/kg ATB200 + 260 mg AT2221 study drug in Stage 2 Period 5.

Compliance based on the number of infusions is calculated as:

100 * (number of infusions administered / number of infusions planned or intended) starting from the first dose of the 20 mg/kg ATB200 + 260 mg AT2221 study drug in Stage 2 Period 5.

Compliance for each subject taking AT2221 will be calculated as:

100 * (total dose administered [mg] / total dose scheduled or planned dose [mg]) starting from the first dose of the 20 mg/kg ATB200 + 260 mg AT2221 study drug in Stage 2 Period 5.

Dose compliance rate will be classified as under-compliance: < 80%, within compliance: 80% – 120%, and over-compliance: > 120%.

10.3. Adverse Events

Treatment-emergent AEs (TEAEs) are defined as AEs whose onset occurs after receiving the study medication. Treatment-emergent AEs that occurred during Stages 1 and 2 have been reported in iCSR-1 and will not be repeated here unless the underlying data have changed.

The SAP describes the events that occurred starting from the administration of 20 mg/kg ATB200 + 260 mg AT2221 in Stage 2 Period 5 through Stages 3 and 4. Events which occur more than 30 days after the last dose of study medication will not be considered as treatment-emergent. Adverse events with an unknown date of onset and a stop date after the start of the study period or unknown will be included as TEAEs. Any AE with a start date equal to the date of first dose, where the time of the AE cannot definitively place the start of the AE prior to the first dose, will be considered as treatment-emergent. If any AE records contain only partial dates, these will be handled by imputation as described in Section 10.1.1. All AEs will be provided in data listings, and those that are treatment-emergent will be flagged in the listings.

Adverse events will be summarized using number and percentage as described in Section 6.2.1. Incidence rate of AEs by patient-years of exposure will also be summarized.

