5. STUDY DESIGN

5.1. Summary of Study Design

This is an open-label, fixed-sequence, single- and multiple-ascending dose, first-in-human (FIH) study to evaluate the safety, tolerability, PK, PD, and efficacy of intravenous ATB200 alone and when co-administered with oral AT2221. The study was conducted in 4 stages and enrolled 4 cohorts as shown in [Table 2](#).

The 4 cohorts in the study are as follows:

- Cohort 1: this cohort was planned to enroll 11 ERT-experienced ambulatory subjects defined as adults with Pompe disease who have been on ERT for 2 to 6 years prior to enrollment and are able to walk at least 200 meters in the 6-minute walk test (6MWT).
- Cohort 2: this cohort was planned to enroll 4 to 6 ERT-experienced non-ambulatory subjects defined as adults with Pompe disease who are wheelchair-bound and unable to walk unassisted and have been on ERT for \geq 2 years prior to enrollment.
- Cohort 3: this cohort was planned to enroll 5 ERT-naïve ambulatory subjects defined as adults with Pompe disease who have never received treatment with ERT and who are able to walk at least 200 meters in the 6MWT.
- Cohort 4: this cohort was planned to enroll 6 to 8 ERT-experienced ambulatory subjects defined as adults with Pompe disease who have been on ERT for at least 7 years prior to enrollment and are able to walk at least 75 meters in the 6MWT. This cohort was added after Amendment 5 to Protocol ATB200-02.

The 4 study stages are as follows:

- Stage 1 is a 3-period, fixed-sequence, single-ascending dose PK study of ATB200 alone. Safety, tolerability, and PK were evaluated following sequential single-ascending doses of 5 mg/kg, 10 mg/kg, and 20 mg/kg of IV infused ATB200 administered 2 weeks apart. Only subjects in Cohort 1 participated in Stage 1.
- Stage 2 is a 2-period, fixed-sequence, single- and multiple-dose PK study of 20 mg/kg ATB200 co-administered with multiple-ascending doses of AT2221. In Stage 2, safety, tolerability, and PK were evaluated following single- and multiple-ascending dose combinations: 20 mg/kg of IV infused ATB200 co-administered with 130 mg of AT2221 administered orally every 14 days (\pm 3 days) for 3 doses, followed by 20 mg/kg of IV infused ATB200 co-administered with 260 mg of AT2221 administered orally for 3 doses. Only subjects in Cohort 1 participated in Stage 2.

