6.4.5. Study Day (Relative Day)

The reference start day is defined for Cohort 1 and for Cohorts 2, 3, and 4 as follows:

- For Cohort 1: Visit 9 (Day 85 in Stage 2, Period 5) is considered the reference start day. This is the day of first dose of the 20 mg/kg ATB200 + 260 mg AT2221 co-administration.
- For Cohorts 2, 3, and 4: The study Day 1 in each cohort is the reference start day.

There will be no Day 0. If the date of interest occurs on or after the reference start day, then the relative study day is calculated as: $(\text{date of interest} - \text{date of reference start day} + 1)$.

Note: The appropriate reference start day should be used depending on whether the summary involves Cohort 1 or Cohorts 2, 3, and 4. For example, for Cohort 1, the relative day of the assessment at V12 will be calculated as: date of V12 – 85 + 1 (ie, Day 43).

If the date occurs before the reference start day, then study day is calculated as: $(\text{date of interest} - \text{date of reference start day})$. Thus, days before the reference start day will have a negative day displacement. For example, for Cohort 1, the relative day of the assessment at the efficacy baseline (V2) will be calculated as: date of baseline assessment – 85.

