10.3.2. TEAEs Reported as Infusion-associated Reaction

For any AE, the reporting investigator is requested to enter onto the AE eCRF whether the AE is deemed to be an IAR and determine its relationship to each of the study drug components (ATB200 and AT2221).

To further characterize TEAEs considered by the reporting investigators to be IARs, a summary table of TEAEs reported as IARs will be provided. The number and percentage of subjects who experienced IARs will be presented by SOC and by PT within SOC. A subject will be counted only once within the same SOC and within the same PT.

A summary of IARs will also be presented for relationship to each treatment component (ATB200 and AT2221) as well as for the co-administration. Additional summary outputs (tables and/or plots) will be provided to describe the clinical characteristics of the IARs by treatment group, including the event rates, changes in intensity over time, and time to first IAR (as described in Section 10.3.3.2). The IAR summary will also be presented by prior history of IARs (yes/no).

A listing that includes treatment-emergent IARs, serious IARs, IAR-related deaths, and IARs leading to study drug discontinuation will be provided. In addition, a listing displaying the number of infusions and infusions that were associated with IARs by each individual subject who had an IAR, will be provided. For each subject, this listing includes subject ID, whether or not pre-medication was given, number of infusions received, number of infusions that were

associated with IARs, percentage of infusions associated with IARs, and a sequential/horizontal listing of the number of IARs corresponding to (or associated with) each infusion.

A summary of the number of subjects with TEAEs that are IARs (ie, IAR-TEAEs), the total number of IARs, and the number of subjects with 1, 2, 3 to 4, or ≥ 5 IARs will be presented.

To characterize the overall number of infusions associated with IARs during the study, the following will be summarized:

- For all subjects (regardless of whether they experienced an IAR), the overall total number of infusions administered during the study, and the number and percentage of infusions administered that were associated with IARs;
- For subjects who experienced IARs, the total number of infusions administered, and the number (and percentage) of infusions administered that were associated with IARs.

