10.3.3. Additional Analysis of IARs

10.3.3.1. Analysis by Onset Intervals

The onset intervals (in months), defined relative to the first dose of the 20 mg/kg ATB200 + 260 mg AT2221 study drug, will be: ≤ 6 , > 6 to ≤ 12 , > 12 to ≤ 18 , > 18 to ≤ 24 , and > 24 . For Cohort 1 subjects, the first dose of the 20 mg/kg ATB200 + 260 mg AT2221 study drug happened in Stage 2 Period 5.

The event rates and changes in intensity over time (over these intervals) will be summarized. This analysis will further describe the clinical characteristics of IARs, and it can help determine whether the IARs disappear over time or appear late.

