10.3.3.2. Analysis of Time to First IAR-TEAE

The number of subjects with IARs and the onset dates of the IARs are already available in the database. For each of these subjects, the time (in weeks) starting from the first dose of the 20 mg/kg ATB200 + 260 mg AT2221 study drug to the onset of the first TEAE that is an IAR (ie, IAR-TEAE) will be calculated as: Time to first IAR-TEAE (weeks) = (date of the first IAR-TEAE while using the 20 mg/kg ATB200 + 260 mg AT2221 dose – date of first dose of the 20 mg/kg ATB200 + 260 mg AT2221 study drug + 1) / 7.

This analysis does not include subjects who have no IARs. The calculated times will be summarized as described in Section [6.2.1](#) to obtain the mean time to the first IAR-TEAE.

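### The by-cohort TEAE and IAR tables and the IAR clock start at Cohort 1's seventh ATB200 infusion but at the first infusion in Cohorts 2 to 4, and no planned table runs from first exposure in every cohort

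*SAP*

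**What the plan says.** SAP section 10.3 fixes the span of the final adverse event tables: "The SAP describes the events that occurred starting from the administration of" the 20 mg/kg ATB200 + 260 mg AT2221 combination in Stage 2 Period 5, and on through Stages 3 and 4. Section 6.4.5 makes the origin explicit. For Cohort 1, "Visit 9 (Day 85 in Stage 2, Period 5) is considered the reference start day"; for the other cohorts, "The study Day 1 in each cohort is the reference start day".

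The IAR timing analyses use the same origin. Section 10.3.3.1 bins onset by months from the first dose of the fixed regimen and notes: "For Cohort 1 subjects, the first dose of the 20 mg/kg ATB200 + 260 mg AT2221 study drug happened in Stage 2 Period 5". Section 10.3.3.2 measures time to first IAR up to the "date of the first IAR-TEAE while using the 20 mg/kg ATB200 + 260 mg AT2221 dose".

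Before Visit 9, Cohort 1 has Stage 1, described in section 5.1 as "sequential single-ascending doses of 5 mg/kg, 10 mg/kg, and 20 mg/kg of IV infused ATB200 administered 2 weeks apart", and then three Period 4 infusions of 20 mg/kg with 130 mg AT2221.

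Section 6.2.2.3 presents the safety results that start at Period 5 by cohort, with a pooled ambulatory column (Cohorts 1, 3 and 4) and a Total (all four). Stage 1 and 2 safety results are shown by dose and are copied from the first interim report unless the data have changed. Section 10.3.2 reports IAR-associated infusions against "the overall total number of infusions administered during the study", without saying when counting begins.

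**The concern.** A column headed Total, or an analysis of the first IAR, will usually be read as running from a subject's first exposure to the investigational enzyme. For Cohort 1, the largest cohort by planned size, it does not.

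This matters most in section 10.3.3.1, whose stated use is to judge whether IARs fade with time or emerge late. Infusions 1 to 6 in Cohort 1 cannot contribute to that judgement. Its earliest onset bin is set beside bins from subjects who are meeting ATB200 for the first time.

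The start is also narrower than the protocol's definition. Protocol section 11.1.1 treats any AE after the first dose of ATB200 and/or AT2221 as treatment-emergent, and section 12.1.1 makes TEAE and IAR counts a primary endpoint. SAP section 11, which tabulates changes from the protocol, does not specifically list the later start. In addition, the Stage 3 and 4 Safety population (SAP section 6.1.2) admits only Cohort 1 subjects who reached Period 5, so anyone who stopped earlier would be outside Total. The documents do not say whether anyone did.

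**Working it through.** **Inputs.** Visit days come from protocol Table 9: Visits 3 to 12 on Days 1, 15, 29, 43, 57, 71, 85, 99, 113 and 127, with an ATB200 infusion at each. Planned sizes come from SAP Table 2: Cohort 1, 11; Cohort 2, 4 to 6; Cohort 3, 5; Cohort 4, 6 to 8.

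**1. The SAP's own figure.** Section 6.4.5 gives Visit 12 as relative Day 43 for Cohort 1. 127 − 85 + 1 = 43, which matches. The re-scaled Month 3 target in SAP Table 4 also matches: 217 − 84 = 133.

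**2. Infusion number at the origin.** Visits 3 to 8 are infusions 1 to 6, so Visit 9 is infusion 7. In Cohorts 2 to 4, Day 1 is infusion 1.

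**3. What the by-cohort tables leave out.**
- Infusions: 11 × 6 = 66 (60 to 72 if Cohort 1 has 10 to 12 subjects).
- Time: 11 × 84 = 924 days; 924 / 365.25 = 2.5 patient-years.

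**4. Share of exposure.** The other cohorts plan 4 + 5 + 6 = 15 to 6 + 5 + 8 = 19 subjects, so the total is 26 to 30.
- Of every subject's first six infusions: 66 / (26 × 6) = 66/156 = 42%, down to 66 / (30 × 6) = 66/180 = 37%.
- Of all infusions to the end of Stage 3, assuming 26 a year and no dropout: Cohort 1 has 6 + 3 + 52 = 61 each and the others 52 each. The totals are 11 × 61 + 15 × 52 = 1,451 and 11 × 61 + 19 × 52 = 1,659. 66/1,451 = 4.5% and 66/1,659 = 4.0%. Stage 4 lowers this further.

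**5. Clock offset in Cohort 1.** 85 − 1 = 84 days = 12.0 weeks = 84/30.4 = 2.76 months.
- The 6, 12, 18 and 24 month cut-points of section 10.3.3.1 fall at about 8.8, 14.8, 20.8 and 26.8 months from first ATB200.
- An IAR at Visit 12 is timed by section 10.3.3.2 at 43/7 = 6.1 weeks. From first ATB200 it is 127/7 = 18.1 weeks.

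**6. Was a Cohort 1 IAR actually left out?** Protocol section 6.4.2.6 reports three IARs in over 400 infusions at the August 2017 cut-off: one in a nonambulatory subject and two in an ERT-naïve subject, so none in Cohort 1. Protocol Table 6 has nine Cohort 1 subjects with Month 18 data (Stage 3 Month 15, target Day 577) at the August 2018 cut-off, which Table 7 dates 3 August. Counting back 576 days puts their Day 1 no later than 4 January 2017 and Visit 9 no later than 29 March 2017, if visits were near target. At least nine of the planned 11 had therefore probably passed infusions 1 to 6 with no reported IAR.

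**The case against.** The strongest defence is that the origin is openly stated and coherent. Stages 3 and 4 concern the fixed 20 mg/kg + 260 mg regimen, and the Safety population, safety baseline, study day, exposure and event counting all share that start. Starting Cohort 1 at Visit 3 would align 5 mg/kg monotherapy with the full combination in the other cohorts. It would not make the cohorts alike either, since Cohorts 1, 2 and 4 all have at least two years of prior ERT. The study is descriptive and each cohort has its own column. This stands, and it is why the Period 5 tables should not be replaced.

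Several stronger readings are tempting, but the documents do not support them.
- *The early events vanish.* They do not. The Stage 1 and 2 tables go into the final report, and section 10.3.1 lists all AEs, with separate listings for deaths, SAEs and discontinuations.
- *A later Cohort 1 IAR will be mislabelled as the first.* The rule would allow it, but step 6 suggests it could not have happened for at least nine subjects.
- *The infusion percentage in section 10.3.2 has mismatched parts.* The wording about the whole study can be read as covering numerator and denominator alike. The fair criticism is that no start is given.
- *Period 5 is counted in both sets of tables.* SAP section 2 says the first interim report focused on safety data from before the fixed regimen. Sections 6.1.2 and 6.2.2.3 place the 260 mg dose within Stage 2. The overlap is unclear.

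**Conclusion.** The point holds as a gap in the planned tables. Total and pooled columns mix subjects counted from their seventh infusion with subjects counted from their first. Cohort 1 onset bins and first-IAR times are displaced by 12 weeks from actual ATB200 exposure, and no planned table cumulates subjects from first exposure across cohorts. The copied by-dose tables do not supply one: a subject can have events in both sets, so subject counts cannot safely be added.

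The size is 66 infusions and about 2.5 patient-years. That is 37% to 42% of the study's first-six infusions, where early reactions would show, but only 4.0% to 4.5% of all infusions to the end of Stage 3. These figures assume planned cohort sizes, visits on target days and, for the last range, no dropout.

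A reader might infer that Cohort 1 IARs have been dropped. The documents do not show that, and the August 2017 data point the other way. What does not depend on IAR numbers is the clock offset, the absence of any early Cohort 1 TEAEs from Total, and the unstated start in section 10.3.2. How many early TEAEs there were is not given.

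**What to change.** 1. Keep the tables that start at Period 5 and label them, including Total and the first-IAR analyses, as *from first 20 mg/kg + 260 mg dose*.
2. Add one cumulative by-cohort table of TEAEs, TESAEs, IARs and deaths from the first ATB200 dose in every cohort (Visit 3 for Cohort 1).
3. Present the analyses in sections 10.3.3.1 and 10.3.3.2 also with time zero at the first ATB200 infusion.
4. In section 10.3.2, state one common start for the numerator and denominator of the infusion percentage.

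The cost is SAP wording and some re-runs on data already collected. The drawback is that the cumulative version mixes the Stage 1 and 2 dose levels within Cohort 1, so it needs a footnote saying so.
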